### 9.3.2. Primary Efficacy Analysis

The primary efficacy endpoint is the change from baseline in serum androstenedione at Week 4. The definitions of the baseline and Week 4 serum androstenedione values that will be used in this analysis are described in Section 6.3.3. The primary analysis of the primary endpoint will be performed using an ANCOVA model, as described in Section 9.2.1. The model will include treatment group, baseline serum androstenedione (as defined in Section 6.3.3), and stratification factors used in the randomization.

Subjects who are missing serum androstenedione at all timepoints at the Week 4 visit will have their data imputed through the multiple imputation procedure described in Section 17.1.

Statistical significance for the treatment comparison will be determined using the multiple comparison procedure described in Section 9.1. Descriptive statistics and LS means will be presented by treatment group along with the LS mean treatment difference, 95% confidence intervals, and p-value.

Descriptive statistics will be presented for serum androstenedione by treatment group and visit from baseline through Week 28. For visits where androstenedione is collected more than once (eg, Day 1; Week 4), the average of the visit values will be analyzed. For visits where more than one pre-morning GC dose sample is collected, the average of the pre-morning GC dose will be analyzed; otherwise, the pre-morning GC dose is the single value collected. Observed and change from timepoint-matched baseline values will be summarized for visit average values and pre-morning GC dose values. The androstenedione observed values from the screening visit will also be summarized.

Mean (±SEM) values of serum androstenedione at each visit will be summarized in line graphs by treatment group. Pre-morning GC dose values and visit average values will be presented on separate plots. Similar graphs will be presented for the changes from baseline.

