#### **Corticosteroids**

During the screening period, subjects should maintain a stable glucocorticoid and (if applicable) mineralocorticoid regimen unless the subject requires glucocorticoid stress dosing for illness or other significant physical stress. The importance of adherence to their glucocorticoid and mineralocorticoid regimen should be emphasized at the first screening visit.

The concomitant administration of certain medications with glucocorticoids can increase the risk of certain adverse effects, including hypokalemic drugs (eg, certain diuretics, amphotericin B), which can increase risk of hypokalemia, and aspirin and salicylates, which can increase the risk of gastrointestinal side effects. Subjects who are on any of these medications for treatment of medical history conditions should be on a stable dose for at least 1 month prior to screening. Use of these medications as well as administration of live vaccines during the study should be avoided to the extent possible.

Subjects who are taking fludrocortisone should maintain a stable fludrocortisone dose to the extent possible during the study. Increases in PRA suggestive of insufficient mineralocorticoid replacement should be managed by first ensuring adequate salt intake before adjusting fludrocortisone dose.

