## 13.4. Sample Size Determination

The sample size of 81 subjects (54 in the crinecerfont treatment group and 27 in the placebo group) is based on a power calculation for the primary endpoint (change from baseline in serum A4 at Week 4). In Study NBI-74788-CAH2001, the mean change from baseline to Day 14 in A4 was -286.2 ng/dL with a standard deviation of 345.02 (pooled across dosing cohorts). Based on a 2-sample t-test with an effect size of 0.83, a sample size of 81 subjects will have greater than 90% power to detect a treatment difference at a 0.05 level of significance. With an effect size as small as 0.70, a sample size of 81 subjects will have greater than 80% power to detect a treatment difference at the same level of significance.

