## 13.6. Statistical Analyses

Descriptive and inferential statistical methods will be used to evaluate and summarize the data from this study. Descriptive statistics refers to the number of subjects (n), mean, SD or SE, median, first (Q1) and third (Q3) quartile, minimum, maximum, and confidence intervals for continuous variables; and refers to the number and percentage of subjects for categorical variables. Inferential statistics refers to the analysis results from hypothesis tests, which will be performed to assess differences between treatment groups (crinecerfont and placebo). The 2-sided level of significance used in this study is 0.05.

In the event that the glucocorticoid dose is alternating, the average dose over 2 consecutive days will be used for glucocorticoid dosing endpoints.

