#### 6.3.3. Baseline Definition of Androstenedione for Primary Endpoint

For subjects  $\geq 6$  years of age with a body weight  $\geq 20$  kg, serum androstenedione at Day 1 and Week 4 was collected 15 minutes before and just prior to dosing with the morning glucocorticoid dose and study drug (Week 4) and 2, 3, 4, and 6 hours after dosing. For subjects who are <6 years of age or with a body weight <20 kg, serum androstenedione at Day 1 and Week 4 was collected prior to the morning dose of glucocorticoid and study drug (at Week 4). Both baseline and Week 4 serum androstenedione values for subjects  $\geq 6$  years of age with a body weight  $\geq 20$ kg will be calculated as the average of all pre-morning glucocorticoid dose serum androstenedione values on Day 1 and Week 4, respectively. Subjects <6 years of age or <20 kg will have only a single pre-morning glucocorticoid dose serum androstenedione value for both baseline and Week 4. If a subject is missing all pre-morning glucocorticoid dose serum androstenedione values at Day 1, the serum androstenedione value collected at the screening visit will be used instead.

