## 9.4. Analysis of Key Secondary Efficacy Endpoints

### 9.4.1. Serum 17-OHP

The first key secondary endpoint is the change from baseline in serum 17-OHP at Week 4. The definition of the baseline and Week 4 serum 17-OHP values that will be used in this analysis are described in Section 6.3.4. The primary analysis of this endpoint will be performed using an ANCOVA model, as described in Section 9.2.1. The model will include treatment group, baseline serum 17-OHP (as defined in Section 6.3.4), and stratification factors used in the randomization. Subjects who are missing serum 17-OHP levels at all timepoints at the Week 4

visit will have their data imputed through the multiple imputation procedure described in Section 17.1.

Statistical significance for the treatment comparison will be determined using the multiple comparison procedure described in Section 9.1. Descriptive statistics and LS means will be presented by treatment group along with the LS mean treatment difference, 95% confidence intervals, and p-value.

Descriptive statistics will be presented for serum 17-OHP by treatment group and visit from baseline through Week 28. For visits where 17-OHP is collected more than once, the average of the visit values will be analyzed. For visits where more than one pre-morning GC dose sample is collected, the average of the pre-morning GC dose will be analyzed; otherwise, the pre-morning GC dose is the single value collected. Observed and change from timepoint-matched baseline values will be summarized for visit average values and pre-morning GC dose values. The serum 17-OHP observed values from the screening visit will also be summarized.

Mean (±SEM) values of serum 17-OHP at each visit will be summarized in line graphs by treatment group. Pre-morning GC dose values and average values will be presented on separate plots. Similar graphs will be presented for the changes from baseline.

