## **17. APPENDICES**

#### 17.1. Implementation of Multiple Imputation for the Primary Endpoint and First Key Secondary Endpoint

For the primary and first key secondary endpoint that require multiple imputation, the following steps will be taken.

1) For subjects on study drug and are missing the endpoint at the timepoint of interest, impute missing data using a regression-based multiple imputation model based on data from subjects with non-missing endpoint data at the timepoint of interest within the same treatment group. The model will include the baseline value for the endpoint, sex, and pubertal stage.

2) For subjects in the crinecerfont treatment group off study drug prior to timepoint of interest and are missing the endpoint at the timepoint of interest, impute missing data using a regressionbased imputation model based on data from Retrieved Dropouts. If there are an insufficient number of Retrieved Dropouts, the endpoint will be imputed from subjects in the placebo treatment group. For similar subjects in the placebo treatment group, missing data will be imputed using non-missing data from subjects in the placebo treatment group. The model will include the baseline value for the endpoint, sex, and pubertal stage.

Note that for the regression-based multiple imputation models described above, the values recorded on the eCRF will be used instead of those recorded at the time of randomization in the IRT.

The number of imputed datasets created from the steps above for each endpoint is 100. After the multiply-imputed datasets have been created, each of the datasets will be analyzed using the ANCOVA model described in Section 9.2.1. The results of these analyses will be combined using PROC MIANALYZE.

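### The two confirmatory Week 4 ANCOVAs omit the pre-dose screening hormone value, a nearly free covariate; the planned intervals may be anywhere from no wider to about 10% wider for it

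*SAP*

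**What the plan says.** The SAP's general model (9.2.1) is `MODEL CHG = TRTP BASE SEX PUBSTAGE`. For the primary endpoint, 9.3.2 states: "The model will include treatment group, baseline serum androstenedione (as defined in Section 6.3.3), and stratification factors used in the randomization". For 17-OHP, 9.4.1 lists treatment group, "baseline serum 17-OHP (as defined in Section 6.3.4), and stratification factors used in the randomization". Protocol 13.6.1.2 and 13.6.1.3 name the same covariates.

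Under SAP 6.3.3 and 6.3.4, BASE is the average of the Day 1 samples taken before the morning glucocorticoid dose. These are two samples about 15 minutes apart, or a single sample in children under 6 years or under 20 kg. The screening value enters only when those Day 1 samples are all missing, in which case "the serum androstenedione value collected at the screening visit will be used instead". Otherwise screening A4 and 17-OHP are only summarized descriptively.

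The screening values exist by design. Inclusion criteria 5 and 6 (Protocol 8.1) set thresholds for pre-dose A4 and 17-OHP, and Protocol 9.8.1.1 collects both. Criterion 4 requires a glucocorticoid regimen stable for at least 1 month before screening, and Protocol 9.10.1 adds: "During the screening period, subjects should maintain a stable glucocorticoid and (if applicable) mineralocorticoid regimen", with stress dosing excepted. The Week 4 imputation models (SAP 17.1) also carry one hormone value: "The model will include the baseline value for the endpoint, sex, and pubertal stage".

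**The concern.** Two samples a quarter of an hour apart do little to average out day-to-day variation in a hormone. The screening sample is the only other pre-treatment day on which A4 and 17-OHP are measured. By accepting it as a substitute baseline, the SAP already treats it as a measure of the same quantity. If it predicts the Week 4 level beyond what Day 1 predicts, leaving it out makes the residual variance larger than it need be on the first two tests of the fixed sequence, in a trial of 81 children. Because the value precedes randomization, adjusting for it does not bias the treatment comparison.

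**Working it through.** **Stated power.** Inputs from Protocol 13.4 and 13.6: 54 and 27 children, two-sided alpha 0.05, and a mean change of minus "286.2 ng/dL with a standard deviation of 345.02". The effect size is 286.2/345.02 = 0.8295, stated as 0.83. The noncentrality is d/√(1/27 + 1/54) = 4.243d.

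- d = 0.83: 3.521, giving power of 94.1% (normal) or 93.6% (noncentral t, 79 df). The plan states more than 90%.
- d = 0.70: 2.970, giving 84.4% or 83.5%. The plan states more than 80%.

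Both statements reproduce, and neither takes credit for any covariate.

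**Precision formula.** Let BY, SY and SB be the within-arm correlations Day 1–Week 4, screening–Week 4 and screening–Day 1. Neither document reports any of them, so all values below are assumptions. Relative to the Week 4 variance:

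- residual variance with Day 1 only: v1 = 1 − BY²
- residual variance with both: v2 = v1 − (SY − BY·SB)²/(1 − SB²)
- excess width of the planned interval: √(v1/v2) − 1

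The gain is zero exactly when SY = BY·SB.

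**Equal correlations (BY = SY = SB = ρ).** At ρ = 0.5, v1 = 0.75 and v2 = 0.75 − (0.5 − 0.25)²/0.75 = 0.6667, so the excess is √1.125 − 1 = 6.1%. The equivalent sample size is 81·v1/v2.

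| ρ | v1 | v2 | Excess width | Equivalent N |
|---|---|---|---|---|
| 0.3 | 0.91 | 0.8615 | 2.8% | 86 |
| 0.5 | 0.75 | 0.6667 | 6.1% | 91 |
| 0.7 | 0.51 | 0.4235 | 9.7% | 98 |

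**Other structures (closed form).**

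| Structure | ρ = 0.3 | ρ = 0.5 | ρ = 0.7 |
|---|---|---|---|
| SY = 0.95ρ, BY = SB = ρ | 2.4% | 4.8% | 6.5% |
| SY = 0.9ρ, BY = SB = ρ | 2.0% | 3.8% | 4.0% |
| SY = 0.8ρ, BY = SB = ρ | 1.4% | 2.1% | 1.0% |
| First-order decay, SY = ρ² | 0% | 0% | 0% |

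If treatment weakens both links to Week 4, with SB = 0.8 and BY = SY = 0.4, 0.5 or 0.6, the excess is 1.1%, 1.9% or 3.3%.

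**Simulation.** Both ANCOVAs were fitted at 54:27 with sex and pubertal stage in the model, so residual df are 81 − 5 = 76 and 81 − 6 = 75 (2,000 runs per scenario). Mean excess widths at ρ = 0.3, 0.5 and 0.7:

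- equal correlations: 2.0%, 5.2%, 9.3%
- equal correlations, entry truncated at the screening median: 0.5%, 1.9%, 4.7%
- first-order decay: −0.6% to −0.7%, so adding screening widens the interval slightly

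**The case against.** The strongest case against is that nothing is wrong with the plan. ANCOVA on baseline and the stratification factors is valid, it matches the protocol, and the stated power holds without any covariate. That stands, so this is an optional gain in efficiency and not a correction.

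The second objection concerns size, and it also stands. A reader might infer that the planned intervals are 3 to 10% too wide as a fact about this trial. The documents do not support that: the range needs equal correlation between all three visits, and several design features point away from it.

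- Screening lasts up to 4 weeks and can be extended by 4 (Protocol 7.1). The sample may therefore precede Week 4 by up to 4 + 4 + 4 = 12 weeks, against 4 weeks for Day 1.
- Screening blood need not be fasting and may be drawn at home.
- Stress dosing is allowed during screening.
- The entry thresholds truncate the screening values.

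These features would tend to reduce the gain; they do not introduce bias. Zero gain requires SY to equal BY·SB. Pure first-order decay is one such case, and it assumes no lasting child-specific level and no sampling noise.

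Third, the change is more than one line of code. The protocol names the covariates, a child with Day 1 missing would have the same number in both covariates, and the Retrieved Dropout imputation group may be too small for another term. These points shape the fix but do not remove the benefit.

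**Conclusion.** The point holds as a missed and essentially free gain in precision on the primary and first key secondary endpoints. Compared with a model that adds the screening value, the planned intervals are:

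- about 3 to 10% wider if all visits correlate equally at 0.3 to 0.7;
- about 0 to 5% wider if the screening-to-Week 4 correlation is clearly lower (0.9 or less of the other two) or if entry truncation matters;
- no wider under pure first-order decay, where adding the covariate costs under 1% of width.

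Every figure rests on assumed correlations. A reader might also infer that the trial is underpowered or its test invalid. Neither follows: power is about 93.6% and 83.5% at the two stated effect sizes, and the planned comparison is unbiased by virtue of randomization.

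**What to change.** Before unblinding:

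1. In SAP 9.3.2 and 9.4.1, prespecify the last screening pre-morning-glucocorticoid value of the same hormone as a second covariate: `MODEL CHG = TRTP BASE SCRN SEX PUBSTAGE`. Taking the last value covers rescreened children. Leave the definition of change from baseline as it is.
2. List the change in SAP section 14, because Protocol 13.6.1.2 and 13.6.1.3 name the covariates.
3. State that a child whose Day 1 value is missing carries the screening value in both BASE and SCRN.
4. Add SCRN to the SAP 17.1 imputation models fitted on completers and on placebo subjects. Add it to the Retrieved Dropout model only if that group is large enough to support it.

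The cost is SAP text and code plus one residual degree of freedom (76 to 75), which raises the t critical value by about 0.02%. No new data or visits are needed.

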### 9.3.3. Sensitivity Analyses of the Primary Efficacy Results

The assumptions relative to the ANCOVA model (eg, linearity, normality) specified for the primary analysis of the primary endpoint will be checked and any violations of these assumptions will be handled through non-parametric statistical methods.

A tipping point sensitivity analysis will be performed to assess the robustness of the missingness assumptions. This sensitivity analysis is based on "delta adjustments" which is a commonly used approach to assess the impact of missing data in clinical trials (O'Kelly and Ratitch, 2014). The imputed Week 4 androstenedione values (from the MI procedure described in Section 17.1) for subjects in both the crinecerfont treatment group and the placebo treatment group will be delta-adjusted (with a range of plausible penalties for each treatment group) until the treatment difference at Week 4 is no longer statistically significant. The implementation procedure for the

tipping point analysis is described in Appendix 17.3. The combinations of delta adjustments that tip the result from statistically significant to insignificant, along with the corresponding insignificant p-values, will be presented in a table and may be presented in a figure.

A complete-case sensitivity analysis will also be performed to test the robustness of the multiple imputation procedure. The ANCOVA analysis for the primary endpoint will be repeated using only subjects with observed data at Week 4. Subjects who are missing the Week 4 primary endpoint will be excluded from the analysis.

Descriptive statistics and LS means for the complete-case sensitivity analyses will be presented by treatment group along with the LS-mean treatment difference, 95% confidence intervals, and nominal p-values.

#### 9.3.4. Supplementary Analyses of the Primary Efficacy Results

The following supplementary analyses of the primary efficacy results will also be performed:

- The percent change from baseline in serum androstenedione at Week 4 will be analyzed using the same method as described in the primary analysis of this endpoint. Missing data will be imputed using the same method as described in the primary analysis of this endpoint.
- The change from baseline in serum androstenedione at Week 4 will be analyzed using the average of all serial sampling androstenedione values at Day 1 and Week 4. If all Day 1 values are missing, then the screening androstenedione value will be used instead. Note that subjects <6 years of age or <20 kg will have only a single serum androstenedione value for both baseline and Week 4. This analysis will be performed using the same method as described in the primary analysis of this endpoint. Missing data will also be imputed using the same method as described in the primary analysis of this endpoint.
- The change from baseline to Week 4 in serum androstenedione, derived as a multiple of the ULN (calculated as observed value divided by the ULN value) [based on age and sex], will be analyzed using the same method as described in the primary analysis of this endpoint. Missing data will also be imputed using the same method as described in the primary analysis of this endpoint.

Descriptive statistics and LS means for the supplementary analyses will be presented by treatment group along with the LS-mean treatment difference, 95% confidence intervals, and nominal p-values.

## 9.4. Analysis of Key Secondary Efficacy Endpoints

### 9.4.1. Serum 17-OHP

The first key secondary endpoint is the change from baseline in serum 17-OHP at Week 4. The definition of the baseline and Week 4 serum 17-OHP values that will be used in this analysis are described in Section 6.3.4. The primary analysis of this endpoint will be performed using an ANCOVA model, as described in Section 9.2.1. The model will include treatment group, baseline serum 17-OHP (as defined in Section 6.3.4), and stratification factors used in the randomization. Subjects who are missing serum 17-OHP levels at all timepoints at the Week 4

visit will have their data imputed through the multiple imputation procedure described in Section 17.1.

Statistical significance for the treatment comparison will be determined using the multiple comparison procedure described in Section 9.1. Descriptive statistics and LS means will be presented by treatment group along with the LS mean treatment difference, 95% confidence intervals, and p-value.

Descriptive statistics will be presented for serum 17-OHP by treatment group and visit from baseline through Week 28. For visits where 17-OHP is collected more than once, the average of the visit values will be analyzed. For visits where more than one pre-morning GC dose sample is collected, the average of the pre-morning GC dose will be analyzed; otherwise, the pre-morning GC dose is the single value collected. Observed and change from timepoint-matched baseline values will be summarized for visit average values and pre-morning GC dose values. The serum 17-OHP observed values from the screening visit will also be summarized.

Mean (±SEM) values of serum 17-OHP at each visit will be summarized in line graphs by treatment group. Pre-morning GC dose values and average values will be presented on separate plots. Similar graphs will be presented for the changes from baseline.

### 9.4.1.1. Sensitivity Analyses

The assumptions relative to the ANCOVA model (eg, linearity, normality) for the first key secondary endpoint will be checked and any violations of these assumptions will be handled through non-parametric statistical methods.

A tipping point sensitivity analysis will be performed to assess the robustness of the missingness assumptions. This sensitivity analysis is based on "delta adjustments" which is a commonly used approach to assess the impact of missing data in clinical trials (O'Kelly and Ratitch, 2014). The imputed Week 4 serum 17-OHP values (from the MI procedure described in Section 17.1) for subjects in both the crinecerfont treatment group and the placebo treatment group will be delta-adjusted (with a range of plausible penalties for each treatment group) until the treatment difference at Week 4 is no longer statistically significant. The implementation procedure for the tipping point analysis is described in Appendix 17.4. The combinations of delta adjustments that tip the result from statistically significant to insignificant, along with the corresponding insignificant p-values, will be presented in a table and may be presented in a figure.

A complete-case sensitivity analysis will also be performed to test the robustness of the multiple imputation procedure. The ANCOVA analysis for the first key secondary endpoint will be repeated using only subjects with observed data at Week 4. Subjects who are missing the Week 4 17-OHP measurement will be excluded from the analysis.

Descriptive statistics and LS means for the complete-case sensitivity analyses will be presented by treatment group along with the LS-mean treatment difference, 95% confidence intervals, and nominal p-values.

